1.0 Background

Chronic pain (CP) affects 100 million individuals in the U.S. CP management has increasingly utilized long-term opioid analgesic therapy, a change associated with increased opioid abuse (via greater exposure in vulnerable individuals), non-pain health consequences (hormone changes, falls), and a dramatic rise in opioid-related overdoses and deaths. Treatment strategies that minimize the need for chronic high-dose opioids are sorely needed. This project will test the novel hypothesis that effective pain relief can be achieved at lower opioid analgesic doses by increasing levels of endogenous opioids (EOs). This hypothesis follows from our prior work demonstrating that analgesic responses to opioid medications are significantly influenced by individual differences in EO activity^{18,19}. Results indicated that for individuals exhibiting higher natural EO levels, morphine produced little incremental analgesic benefit. In contrast, for those displaying less natural EO analgesia, morphine produced significant analgesia. Findings suggested that morphine in effect supplemented lower levels of EO analgesia, making pain responses of individuals lower in EO function who had received morphine look statistically similar to individuals higher in EO function not receiving morphine¹⁸. An Opioid Supplement Model was suggested, in which opioid analgesics supplement EO function, making up the difference necessary to maximize opioid receptor-mediated pain inhibition. Our previous work looked only at natural variations in EO function, and only at a single opioid analgesic dosage. Therefore, the key clinical implication of the Opioid Supplement Model has not been tested: can effective pain relief be achieved at lower opioid analgesic dosages by enhancing EO function? This is one primary aim of the current proposal. While several controlled trials indicate that aerobic exercise is effective for reducing CP intensity, and it is widely assumed these benefits are related to enhanced EO analgesia, this assumption has received surprisingly little empirical testing. Therefore, a second aim of this project is for the first time to directly test whether aerobic exercise training enhances EO function in individuals with chronic low back pain (CLBP), and whether resulting reductions in CP intensity are attributable to these EO changes. Results will provide important information on mechanisms underlying a common CP therapy and have potentially important implications for public health, as results would highlight the potential for strategic combination of lower dose opioid analgesic therapy with nonpharmacological EO-enhancing interventions, potentially reducing negative side effects and mitigating opioid therapy risks.

2.0 Rationale and Specific Aims

Daily use of high-dose opioid analgesics for CP management has increased dramatically, and is associated with increasing numbers of patients experiencing opioid-related negative health effects, abuse, overdose, and even death. Ways of providing effective chronic pain relief with less reliance on high-dose opioid analgesics are sorely needed. Based on recent work indicating that responses to opioid analgesics are influenced by functioning in endogenous opioid systems^{18,19}, this project will determine whether enhancing endogenous opioids (via aerobic exercise training) permits achieving desired levels of analgesia with lower dosages of opioid analgesics, and fewer side effects and abuse-relevant drug effects. This 4 year project will test study hypotheses in a sample of 116 chronic low back pain patients. The study will have two key elements: 1) a randomized, controlled aerobic exercise manipulation in CP patients completing daily

electronic pain diaries and 2) laboratory evoked thermal pain protocols pre- and post-exercise permitting direct examination of changes in both opioid analgesic effects (in response to a series of incremental morphine doses) and EO activity (indexed by comparing pain responses after placebo vs. opioid blockade). This design will permit testing the novel hypothesis that aerobic exercise can facilitate desired analgesia levels at lower dosages of opioid analgesics via enhanced EO function.

1) *To determine whether an aerobic exercise manipulation increases EO activity in CLBP patients, and whether these EO changes mediate manipulation-induced reductions in evoked pain responsiveness and daily CP intensity.* If hypotheses are supported, a) participants randomized to exercise will exhibit greater decreases in CP intensity and evoked pain responsiveness and greater increases in EO function (indexed by laboratory responses to opioid blockade) than those assigned to the control condition, and b) the indirect path linking the exercise condition to reduced CP intensity via increased EO function will be significant.

2) *To determine whether the exercise manipulation is related to achieving analgesic targets at lower opioid analgesic dosages, and whether these changes in analgesic requirements are mediated by pre-post EO changes.* If hypotheses are supported, a) participants assigned to exercise will exhibit a 25% reduction in acute pain responses (relative to pre-manipulation placebo responses) at a significantly lower total morphine dose (based on incremental dosing) than controls, and b) the indirect path linking the exercise condition to reduced morphine requirements via increased EO function will be significant.

3) *To determine whether the exercise manipulation is related to achieving a 25% morphine-induced reduction in evoked pain responsiveness with fewer negative side effects and abuse-relevant effects, and whether these changes are mediated by pre- to post-manipulation EO changes.* If hypotheses are supported, a) participants assigned to the exercise condition will exhibit a 25% reduction in acute pain responses (relative to pre-manipulation placebo responses) during morphine administration with significantly fewer negative side effects (e.g., nausea, sedation) and less abuse-relevant subjective drug effects (e.g., drug liking, euphoria) than those in the control condition, and b) the indirect path linking the exercise condition to reduced side effects and abuse-relevant effects via increased EO function will be significant.

3.0 Animal Studies and Previous Human Studies

Both EOs and opioid medications produce analgesia through activating the same opioid receptors. This common mechanism of action between EO analgesia and responses to opioid-based medications suggests that the former may be related to the latter. Surprisingly, until recently this question had never been directly addressed in humans, although indirect evidence did support these hypothesized associations. For example, a systematic review of randomized acupuncture trials found that acupuncture not only significantly reduces postoperative acute pain, but also reduces opioid analgesic consumption and opioid side effects¹¹². To the extent that the effects of acupuncture are EO-mediated, as suggested by several studies indicating its analgesic effects can be blocked by opioid antagonists^{57,58,113}, these findings imply that enhancing EO function

might supplement analgesia gained from opioid-based medications and thus permit reduced dosages.

The Co-PIs recently reported the first human work directly examining associations between EO function and opioid analgesic responses. Using controlled laboratory methods, associations were examined between spontaneous EO function (indexed by differences in acute pain responses between opioid blockade [naloxone] and placebo conditions) and analgesic responses to morphine, the prototypic mu opioid agonist¹⁸. In a sample of 45 chronic low back pain patients and 31 pain-free healthy controls (combined for analyses given no significant main or interaction effects of subject type), significant associations were observed between EO function and morphine analgesic responses on all 7 measures of pain responsiveness examined across two different evoked pain tasks (ischemic pain, thermal pain)¹⁸. We recently extended these findings to clinical chronic pain¹⁹. Individuals exhibiting less EO inhibition of their chronic back pain (less effect of opioid blockade on back pain intensity) experienced greater relief of their back pain with morphine administration relative to higher EO individuals¹⁹. To isolate the source of the effects noted in Bruehl et al.¹⁸ and provide a clear means of portraying them, median splits were conducted on EO function variables derived for each pain measure, with placebo condition and morphine condition responses for each measure then compared across the resulting groups. The pattern of results indicated an intriguing source of these observed associations. First, as expected, when EO systems were intact (placebo condition), individuals exhibiting relatively lower spontaneous EO activity were significantly more responsive to both evoked pain tasks on all measures. Second, individuals with lower EO function exhibited substantial morphine analgesic responses whereas those with higher EO function did not.

A key finding in Bruehl et al.¹⁸ was that morphine reduced evoked pain responsiveness among individuals lower in EO function to levels statistically comparable to those observed in participants with higher spontaneous EO function *in the absence of any morphine*. We propose that these findings fit what we term an "opioid supplement model," in which opioid analgesics supplement EO function, making up the difference necessary to maximize opioid receptor-mediated pain inhibition. If the opioid supplement model is valid, then the desired degree of pain relief might be obtained by a combination of lower EO activity and higher amounts of opioid analgesics, or conversely – and in most cases preferably - higher EO activity and lower amounts of opioid analgesics. In this latter context, we propose that aerobic exercise may be used to enhance EO function, with subsequent beneficial effects on the dose of opioid analgesic needed to achieve desired pain relief.

Rationale for use of an aerobic exercise manipulation to enhance EO function derives from several sources. First, aerobic exercise is used clinically in CP management, and results of a number of controlled studies document that it significantly reduces evoked pain responses and clinical pain intensity in CP patients^{46,72,94,103,107}. Second, a review by Co-Inv [name] documents the analgesic effects of exercise with regard to laboratory evoked pain responses⁷⁶, with several opioid blockade studies conducted in individuals free of CP supporting a role for enhanced EO activity in these effects^{55,68,74,98,99}. These latter studies demonstrated that reductions in evoked pain responsiveness induced by acute exercise when healthy subjects are administered placebo do not occur when EO function is blocked by pharmacological opioid antagonists. Third, recent brain imaging research also supports these findings,

indicating that an acute exercise manipulation reduced evoked pain responses and enhanced pain-related brain activations in an important EO pain modulatory brain region (periaqueductal gray), with parallel increases in circulating levels of beta-endorphin, a key EO analgesic¹⁰⁴. Fourth, potential importance of EO mechanisms in reducing CP via regular aerobic exercise training is suggested by opioid blockade work in animals. Regular exercise (from 5 days to 5 weeks) was found to significantly reduce, via EO mechanisms, behavioral indicators of CP in animal models of chronic muscle pain and neuropathic pain^{6,110}. Interestingly, significantly increased brain levels of beta-endorphin were noted during the exercise period, with exercise-related analgesia persisting for 5 days following exercise discontinuation¹¹⁰. The latter finding is particularly intriguing, as it suggests that regular aerobic exercise training may enhance EO function not only immediately after acute exercise, but for an extended period of time after acute exercise has ceased. Recently published work in humans further indicates that self-reports of greater physical activity, including exercise, is associated with enhanced conditioned pain modulation⁹⁶, a marker of descending pain inhibitory function which some work suggests has an EO-mediated component^{75,122}.

Plasma endocannabinoid levels will be assayed in vitro from blood samples obtained in the study. Endocannabinoids can produce analgesia, may potentially interact with and influence opioid responses (thus serving as a potential confound to tests of primary study hypotheses), and may represent a previously unexplored mechanisms of change for analgesic effects of exercise.⁷³ .

4.0 Inclusion/Exclusion Criteria

Inclusion criteria for study participation will be:

- Intact cognitive status and ability to provide informed consent
- Ability to read and write in English sufficiently to understand and complete study questionnaires
- Age 18-55 inclusive
- Presence of persistent daily low back pain of at least three months duration and of at least a 3/10 in average intensity

Exclusion criteria will be:

- Engagement in > 2 days/wk and > 60 min/wk of moderate or vigorous intensity activity based on responses to 6 validated survey questions at screening (CDC BRFSS), and confirmed by exercise-specific questions in the electronic diary obtained prior to the exercise intervention period
- History of renal or hepatic dysfunction
- Current or past alcohol or substance dependence
- A history of PTSD, psychotic, or bipolar disorders
- Chronic pain due to malignancy (e.g., cancer), autoimmune disorders (e.g., rheumatoid arthritis, lupus), or fibromyalgia
- Recent daily opiate use
- Use of any opioid analgesic medications within 72 hours of study participation (confirmed through rapid urine screening conducted prior to study participation)
- Females who are pregnant
- History of cardiovascular disease (including myocardial infarction)
- History of seizure disorder

- Prior allergic reaction/intolerance to morphine or its analogs
- Presence of cardiac disease or any other medical condition that would make engaging in the aerobic exercise manipulation unsafe

5.0 Enrollment/Randomization

Participants will be recruited from a list of potentially qualifying participants from past studies in our lab who had previously indicated a desire to be contacted about future studies, as well as via local newspaper advertising, posted flyers (including at the Vanderbilt Interventional Pain Center and the Osher Center for Integrative Medicine at Vanderbilt), and e-mail advertisements distributed throughout campus via the Vanderbilt mass e-mail system. Interested individuals will be able to contact the designated study research assistant by phone or e-mail. Random assignment to both study conditions will be stratified by community vs. clinic population recruitment source to control for possible influence of this variable on results. Approximately equal numbers of males and females of all races will be recruited for the study. Individuals expressing an interest will first be provided verbally with information on the study procedures, risks, and benefits, and if interested, will be given the opportunity to read the IRB-approved informed consent form. All questions from potential subjects will be answered by the study representative as accurately as possible. All individuals agreeing to participate will provide written informed consent prior to beginning any study procedures. Subject recruitment and consent procedures will be carried out by individuals designated and trained by the PIs and the IRB to carry out these procedures (i.e., the research assistant).

The study will employ a mixed between/within-subjects design using double-blind, counterbalanced, placebo-controlled administration of both an opioid antagonist (naloxone) and an opioid agonist (morphine). The study will use a 6 week supervised aerobic exercise manipulation, with subjects randomly assigned to the exercise protocol or a no exercise control condition. All participants will undergo three identical laboratory pain-induction sessions (each \approx 5 days apart) prior to randomization to experimental condition, and again at the end of the 6 week exercise manipulation period (regardless of exercise group assignment) during which they will receive the 3 study drugs and participate in controlled laboratory evaluation of evoked thermal pain responsiveness.

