Exercise Manipulation Protocol: Participants randomly assigned to the exercise training group will undergo aerobic exercise training 3 times/wk for 6 wks. To enhance and monitor adherence, all of the exercise sessions will be conducted at the Dayani Center and supervised by ACSM certified personal trainers thoroughly trained in study procedures. Each exercise session will consist of a 5 minute warm-up, 30 minutes of aerobic exercise, followed by a 5 minute cool-down period. Aerobic exercise will consist of treadmill walking/running, stepping, elliptical, or cycling exercise as preferred by the participant. This will allow participants to choose the type of aerobic exercise most tolerable to them to minimize symptom exacerbation (i.e., acute increases in pain) while maximizing adherence to the training program. Effort levels across the different types of aerobic exercise will be standardized using heart rate (HR) and perceived exertion (RPE) monitoring as recommended by the American College of Sports Medicine (ACSM). Target heart rate zones will be established using the Karvonen formula and heart rate reserve (HRR). Duration of exercise will be standardized at 30 minutes with a target exercise intensity between 70-85% HRR (RPE = 15, hard). Because of the focus on de-conditioned individuals with CLBP, the duration and intensity of exercise will be progressively increased up to target during the first two weeks to avoid symptom exacerbation and minimize study drop-out. Participants will begin with 10-15 minutes of exercise between 40-55% HRR (RPE = 11-12, light) during the first week, 20-30 minutes of exercise between 55-70% HRR (RPE = 12-13, somewhat hard) during the second week, and then 30 minutes of exercise between 70-85% HRR (RPE= 14-16, hard) for the duration of the study. To ensure that participants are exercising within their prescribed workload during each session, HR and RPE will be assessed and recorded every 5 minutes during exercise using Polar HR monitors and Borg's 6-20 RPE scale. In addition, pain will be assessed every 5 minutes during exercise using a pain rating scale developed for this purpose to monitor back pain, with adjustments to the workload in the event of back pain during exercise.

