The PI and co-investigators will carefully monitor adherence to the study protocol on a regular basis via direct supervision, monitoring of obtained study materials, and regular study team meetings. All adverse events and unanticipated problems will be immediately communicated across the two study sites. Deviations from protocol will be immediately corrected, and if appropriate, will be reported to the IRB and the program officer at NIH/NIDA (sponsoring agency).

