Effect sizes ranged from $d=.6$ to $d=1.2$ in directions indicating that opioid blockade reduced post-exercise analgesia, suggesting that EO function partly mediated the effect of acute exercise on pain intensity. The mean effect size across these studies for the impact of EO mechanisms on exercise-related analgesia was $d= .93$ (equivalent to $r=0.42$). This effect size is key to initial analyses of Specific Aim 1. The proposed sample size will result in a power exceeding 0.90 for testing effects of the exercise manipulation on EO function (two-sided $p<.05$ significance criterion). Effect size estimates for the b path in the mediational model reflecting influences of EO function on morphine responses can be derived from our prior work, which indicated an average effect size of $r=0.27$ for associations between natural variations in EO function (opioid blockade effects) and analgesic responses to a single morphine dose across all pain measures and both laboratory evoked pain tasks¹⁸. Effect size for the b path reflecting influences of EO function on chronic back pain intensity can be estimated from Bruehl et al.²⁵, with an effect size of $r=0.26$ for associations between EO analgesic function in the laboratory and diary ratings of chronic back pain intensity (greater EO function was associated with lower daily back pain intensity). Given these effect sizes for the a and b paths in the mediation model, the total sample size for the proposed project was selected as $n=116$, resulting in a power of 0.80 (two-tailed $p<.05$ criterion for significance) for testing mediation effects hypothesized in Aims 1-3 using the proposed bootstrap approach (based on Fritz and MacKinnon⁶⁴).

Data Reduction and Analyses

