Secondary exploratory analyses will examine potential moderator effects of sex and BL EO function on effects observed in primary analyses. These analyses will test whether the direction and magnitude of Group effects and/or Group x Time interaction effects for DVs depend on the sex of the participant and/or on degree of BL EO analgesia. To illustrate, GLM procedures will be used to test for a significant Group x Time x BL EO function interaction effect for morphine dosage outcomes in Aim 2. If significant, simple effects will be used to test whether Group was related to changes in required morphine dosages from BL to post-manipulation differently for those low vs high in BL EO function. Within the exercise group only, we will also examine associations between exercise intensity (i.e., average number of minutes \geq target 70% HRR during sessions) and pre-post manipulation EO changes and changes in morphine responsiveness. Finally, we will test whether: a) BL depression and anxiety symptoms predict analgesic responses; b) the exercise manipulation reduces these symptoms; c) such changes contribute to manipulation-related changes in analgesic responses.

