11.0 Privacy/Confidentiality Issues

All published data will be reported in a manner in which individual data for specific subjects are not identifiable. Data will be coded on paper and in the computer by subject number rather than name to help further insure confidentiality. All hardcopy study records from each site will be maintained in a filing cabinet in a locked office at each PI's office suite, and will be accessible only to the principal investigators and their designees. All other subject data records will be maintained on password-protected computers stored in the locked offices of each PI. Hardcopies of the data will be maintained for 6 years, after which they will be destroyed.

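### The Aim 1-3 models contain neither the randomisation stratum nor sex, nor site if both sites randomise, which leaves removable variance and an open route to confounding of the mediation b path

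*Combined protocol and SAP*

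**What the plan says.** Section 5.0 names one stratum: "Random assignment to both study conditions will be stratified by community vs. clinic population recruitment source". Section 6.0 repeats it where randomisation after the third laboratory visit is described. The stated purpose is to control any influence of recruitment source on the results.

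Two passages imply more than one site. Section 8.0 states that "All adverse events and unanticipated problems will be immediately communicated across the two study sites", and section 11.0 that "All hardcopy study records from each site will be maintained in a filing cabinet". Yet every recruitment channel in section 5.0 that names an institution belongs to one institution, and section 6.0 says that "all of the exercise sessions will be conducted at the Dayani Center". The second site's role is not described.

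Section 10.0 specifies Group x Time mixed ANOVAs for Aims 1 and 2, with Aim 3 in parallel, followed by bias-corrected bootstrap mediation of pre-post changes. No primary model names recruitment source, sex or site. The only candidate covariate is exercise minutes in the post-intervention diary, which is measured after randomisation. Sex appears only in exploratory work on "potential moderator effects of sex and BL EO function on effects observed in primary analyses". On sample size, "the total sample size for the proposed project was selected as $n=116$, resulting in a power of 0.80" for the mediation tests.

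**The concern.** The plan treats recruitment source as important enough to stratify on and then leaves it out of every stated model. It treats sex as a recruitment target and a possible moderator, but adjusts no primary model for it. It mentions two sites and assigns them no analytic role.

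Two things are at stake. Outcome variance explained by these factors stays in the error term. More importantly, randomisation protects the a path (exercise to EO change) but not the b path (EO change to outcome change). A baseline factor related to both changes is an ordinary confounder of b, and the project is powered specifically for the test that depends on b. The plan would also read a significant indirect path as evidence of an opioid mechanism, and a direct path alone as evidence of a non-opioid one.

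**Working it through.** **Inputs from section 10.0.** N = 116; a path d = 0.93 (r = 0.42); b path r = 0.26 to 0.27; two-sided 0.05; stated mediation power 0.80. Section 7.0 assigns half the participants to exercise, so 58 per arm.

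**Inputs assumed.** The split of the factor (50:50 unless stated) and its effect on pre-post change. The documents give neither.

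**1. The plan's own figures.** r = d/sqrt(d² + 4) = 0.93/sqrt(0.8649 + 4) = 0.42. Simulating the bias-corrected bootstrap at N = 116 with a binary group gives power 0.795 for both b = 0.26 and b = 0.27. The stated 0.80 reproduces. Power for the a path is 0.999, consistent with the stated figure above 0.90.

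**2. Chance imbalance and the group contrast.** For a 50:50 factor, the count in one arm is hypergeometric with SD sqrt(58 x 0.25 x 58/115) = 2.70. The arm difference in proportion has SD 2 x 2.70/58 = 0.093, or 9.3 points. The chance of a difference of at least 10 points is 0.35; of at least 20 points, 0.04. The shift in the group difference is imbalance x effect on change:

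| Imbalance | Effect 0.2 SD | Effect 0.5 SD |
|---|---|---|
| 10 points | 0.02 SD | 0.05 SD |
| 20 points | 0.04 SD | 0.10 SD |

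Against a planned d of 0.93 this is small, and its expectation is zero.

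**3. Confounding of the b path.** Let a 50:50 factor F shift both changes by s within-level SDs in the same direction, with no true b path:

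EO change = 0.93 x group + s x F + e1; outcome change = s x F + e2.

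Given group, the induced correlation is 0.25s²/(1 + 0.25s²). At s = 0.5 it is 0.0625/1.0625 = 0.06; at s = 0.8 it is 0.16/1.16 = 0.14. The planned b is 0.26 to 0.27. The same expression is the share of variance that a model term would remove: 6% and 14%.

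False-positive rate of the bias-corrected 95% interval (58 per arm, F allocated at random, 3,000 trials, 1,000 resamples, simulation SE 0.005 to 0.009):

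| Assumed shift s | No term for F | Term for F |
|---|---|---|
| 0 | 0.07 | 0.07 |
| 0.2 | 0.07 | 0.08 |
| 0.3 | 0.09 | 0.07 |
| 0.5 | 0.14 | 0.08 |
| 0.8 | 0.38 | 0.08 |

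Smaller runs of this scenario gave 0.12 to 0.16 without the term and 0.08 to 0.11 with it at s = 0.5, and 0.37 to 0.38 against 0.08 at s = 0.8. The method runs somewhat above 0.05 even at s = 0, so the comparison is between columns.

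The plan tests mediation only where the group effect on the outcome is significant. Adding a direct exercise effect to the outcome equation leaves the estimated indirect effect unchanged, because group is already in that equation. The rates therefore describe an outcome that exercise improves by a non-opioid route strongly enough to pass that precondition.

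**4. Cost of adjustment.** At a 20-point imbalance the variance of the group effect rises by 1/(1 - 0.2²) = 1.042. Before any gain from explained variance, a-path power moves from 0.999 to 0.998 at d = 0.93, and from 0.898 to 0.886 at d = 0.6.

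**The case against.** The case on the other side is substantial, and much of it stands.

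- **A reader might infer that participants are randomised at two sites.** The documents do not show this. Section 8.0 concerns communication of adverse events and section 11.0 concerns storage of records; the named recruitment and exercise locations are in one place. The site part is conditional.
- **A reader might infer that trainers differ by site.** Section 6.0 puts all exercise sessions at one centre, so as written they do not.
- **A reader might infer that sex enters no model.** It enters the exploratory moderator analyses. It is absent only from the primary and mediation models.
- **A reader might infer that chance imbalance biases the exercise effect.** Under randomisation it does not in expectation, and it does not inflate the type I error of that contrast. Baseline sessions precede randomisation and the analyses use pre-post change, so stable differences in equipment, testers or patient mix cancel. Only a difference in change can matter.
- **A reader might want sex as a stratum.** The gain is negligible. With 34 women in one arm and 24 in the other, mirrored for men, the variance of the Group x Sex contrast rises from 4/29 = 0.138 to 2/34 + 2/24 = 0.142, about 3%. Crossing site, source and sex would give eight cells averaging 14.5 participants. With assignment evident to participants and trainers, small blocks in such cells could make allocations easier to predict.

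None of this answers the b-path point. Differencing removes stable levels, not a factor's effect on change, and randomising group does not randomise EO change. Nor does it explain why the stratum is missing from the models.

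**Conclusion.** The concern holds as a gap in model specification, not as a failure of randomisation. Recruitment source and sex are known at baseline, and no Aim 1-3 group or mediation model adjusts for either. Site has no analytic role and its status is unclear.

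The effect on the exercise contrast is small: 0.02 to 0.10 SD at imbalances of 10 to 20 points and assumed effects of 0.2 to 0.5 SD, against a planned 0.93. The effect on the mediation test depends on how far a factor moves both changes. It is negligible up to about 0.3 SD, modest at 0.5 SD (0.14 against 0.08) and serious at 0.8 SD (0.38 against 0.08). These shifts and the 50:50 split are assumptions, and the true gain may be small. The case for adjusting rests on its low cost and on the central place of the mediation test. The stated power and N = 116 are not in dispute.

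**What to change.** In section 10.0, prespecify recruitment source and sex as fixed covariates for Aims 1-3:

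- **Group models.** Include each covariate with its interaction with Time, or analyse the change score with the covariates as main effects. In a Group x Time ANOVA, a covariate without its Time interaction does not adjust the Group x Time contrast.
- **Mediation models.** Put the same covariates in both equations: EO change on group, and outcome change on group and EO change.

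State in sections 8.0 and 11.0 what the second site does. If both sites randomise participants, add site as a covariate in the same models, stratify allocation by site x recruitment source (four cells, averaging 29 participants), and reconcile this with the single exercise location in section 6.0. If the second site does not enrol, say so. Sex does not need to become a stratum.

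The cost is two model degrees of freedom, or three with site, plus a new allocation list only if site applies. N is unchanged. If allocation has started, the covariates can still be fixed before outcomes are seen by arm.
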